## 1 INTRODUCTION

The purpose of this SAP is to outline the planned analyses to be completed to support the completion of the Clinical Study Report (CSR) for protocol CLIN-60120-452. It describes the rules and conventions to be used in the analysis and presentation of data, the data to be summarised and analysed, including specificities of the statistical analyses to be performed.

A separate shell will be provided for tables, figures and listings.

The SAP is to be finalised prior to database lock (DBL). Any deviations from the SAP after database lock will be documented in the CSR (section 9.8 “Changes in the conduct of the study or planned analyses” as per International Conference on Harmonisation (ICH) E3).

## 2 PROTOCOL OVERVIEW

The aim of Study CLIN-60120-452 is to provide continued access to palovarotene once the ongoing clinical studies have ended. More specifically, the aim is to provide treatment continuity to participants who have completed one of the parent studies (Study PVO-1A-301 or PVO-1A-202 (Parts C and D correspond to Study PVO-1A-204 in France)) and, in the investigator’s judgement, may benefit from palovarotene therapy until palovarotene is reimbursed in the country where the study is being conducted, or another access programme becomes available, or until the study end date of November 2024 is reached, whichever occurs first.

### 2.1 Study Objectives and Hypotheses

The objectives of the study are as per the table below:

Objectives	Endpoints
Primary	
 
To further evaluate the safety of palovarotene in adult and paediatric participants with FOP.
 
 
 
Incidence and description of all treatment-emergent adverse events (TEAEs) whether or not they are considered as related to the study intervention;
 
Incidence and description of all serious and nonserious treatment-related TEAEs;
 
Incidence and description of all serious TEAEs, whether or not they are considered as related to the study intervention;
 
Incidence and description of all nonserious TEAEs whether or not they are considered as related to the study intervention.
 

Secondary	
 
To describe range of motion, as assessed by the Cumulative Analogue Joint Involvement Scale (CAJIS) for FOP, at the Inclusion Visit and over time under palovarotene treatment;
 
Raw values and change from the Inclusion Visit in CAJIS total score at each Follow-up Visit;
 
To describe the use of assistive devices and adaptations for daily living by FOP participants, at the Inclusion Visit and over time under palovarotene treatment;
 
Raw values and shift from the Inclusion Visit in the use of assistive devices and adaptations for daily living at each Follow-up Visit;
 
To describe physical function, using the adult form of the FOP Physical Function Questionnaire (FOP-PFQ), at the Inclusion Visit and over time under palovarotene treatment;
 
Raw values and change from the Inclusion Visit in % of worst score for total score, upper extremities subscore and mobility subscore using the adult form of the FOP-PFQ for all participants, at each Follow-up Visit;
 


 
To describe the FOP healthcare utilization in patients with FOP
 
To describe the parameters of lung function (observed and % predicted forced vital capacity (FVC), observed and % predicted forced expiratory volume in one second (FEV1), absolute and predicted FEV1/FVC ratio, observed and % predicted diffusion capacity of the lung for carbon monoxide (DLCO)) at the Inclusion Visit and over time under palovarotene treatment;
 
	
 
Type and frequency of healthcare utilization
 
Raw values and change from the Inclusion Visit in observed and % predicted FVC at each Follow-up Visit;
 
Raw values and change from the Inclusion Visit in observed and % predicted FEV1 at each Follow-up Visit;
 
Raw values and change from the Inclusion Visit in absolute and predicted FEV1/FVC ratio at each Follow-up Visit;
 
Raw values and change from the Inclusion Visit in observed and % predicted DLCO at each Follow-up Visit;
 

 
To describe physical and mental health, using the adult form of the Patient Reported Outcomes Measurement Information System (PROMIS) Global Health Scale, at the Inclusion Visit and over time under palovarotene treatment;
 
	
 
Raw values and change from the Inclusion Visit in physical and mental function (mean global physical and mental health score converted into T-scores), using the adult form of the PROMIS Global Health Scale for all participants, at each Follow-up Visit;
 

 
To describe the number of investigator-reported flare-ups, flare-up outcomes (extra bone growth, restricted movement) and flare-up duration by body location and overall;
 
	
 
Raw values and change from the Inclusion Visit in number of investigator-reported flare-ups, flare-up outcomes (extra bone growth, restricted movement) and flare-up duration at each Follow-up Visit by body location and overall;
 
Percentage of participants with extra bone growth associated or not with a flare-up status at each Follow-up Visit;
 


In relation to FOP (via interviews):
 
 
To further understand and describe participants' experiences with FOP symptoms (e.g. flare-ups, joints being locked);
 
To describe the overall impact of the disease on participants living with FOP (e.g. physical functioning, emotional health, social functioning, work/school/daily life impacts);
 
To identify and rank the critical joints from a participant's perspective;
 
	
 
Not applicable.
 

In relation to patient experiences with palovarotene in the parent study :
 
 
To further understand and describe participant experience with palovarotene (e.g. decrease in number of flares up, delay in physical disability, overall satisfaction)
 
To describe the emotional benefit for participants of using palovarotene as a treatment for FOP;
 
To assess participants' perceptions of benefits and risks of palovarotene.
 
	

## 2.2 Overall Study Design and Investigational Plan

Study CLIN-60120-452 is a multicentre, noncomparative rollover study with the aim of continuing to provide palovarotene to participants with FOP who have completed one of the

parent studies (Study PVO-1A-301 or PVO 1A 202/PVO 1A 204) and, in the investigator's judgement, may benefit from palovarotene therapy. Participants who have completed the parent study are defined as those who have completed the parent End of Study (EOS) or End of Treatment Visit.

[figure not shown]
The study is designed primarily to further evaluate the safety of palovarotene and secondly, to collect efficacy data in male and female participants aged  $\geq 14$  years (qualifying as skeletally mature or, based on investigator's assessment, have reached final adult height) with FOP treated with palovarotene.

Participants are eligible for the study whether they are receiving chronic or flare-up treatment in the parent study at the time of transition. Participants who previously interrupted/stopped palovarotene treatment and are currently under parent study follow-up due to the premature physeal closure (PPC) related partial clinical hold in participants  $<14$  years, are eligible for the study if they are  $\geq 14$  years of age and skeletally mature/have reached final adult height based on investigator's assessment. There must be a current parent study signed informed consent (ICF) form for the participant to be eligible for Study CLIN-60120-452.

A maximum of 87 participants from studies PVO-1A-301, PVO-1A-202/PVO-1A-204 are eligible to be enrolled and will receive palovarotene once daily at the dose received during their participation in the parent study at the time of transition to Study CLIN-60120-452 or prior to interrupting/stopping palovarotene treatment.

The study will consist of an Inclusion Visit (Day 1) (which ideally corresponds to the parent EOS Visit), a continuous dosing treatment period (including a Follow-up Visit every six months), and an EOS/Early Withdrawal (EW) Visit. The maximum duration is three years from enrolment to last study visit (November 2021 to November 2024). The study schema is below:

**Figure 1 Study Schema**

eCRF=electronic case report form; EOS=End of Study; EW=Early Withdrawal.

- a. For any assessments already performed at the parent study EOS Visit, the study site will enter the data again in the Study CLIN-60120-452 eCRF. Participants who completed the paediatric versions of the questionnaires at the EOS Visit of the parent study are required to complete the adult versions of the questionnaires at the CLIN 60120 452 Inclusion Visit.
- b. Treatment will be individualised for each participant and based on the regimen (chronic or flare-up treatment) and the dose received in the parent study at the time of transition to Study CLIN-60120-452 or prior to interrupting/stopping palovarotene treatment. Participants will be supplied with chronic treatment as well as the appropriate dose of palovarotene to initiate flare-up treatment when a flare-up or traumatic event is confirmed by the investigator. If a participant is instructed by the investigator to reduce the daily dose of palovarotene due to intolerable adverse reactions but does not have the appropriate dose in his/her possession, the study site will make immediate arrangements to ship the appropriate palovarotene dose to the participant.

Eligible participants will ideally enter the study directly after completing the EOS Visit of the parent study (Study PVO-1A-301 or PVO-1A-202/PVO-1A-204) and the ICF is signed. Any study assessments already performed at the parent EOS Visit will serve as the Inclusion Visit assessment for Study CLIN-60120-452 (maximum of one month allowed between the two visits). Treatment initiation for Study CLIN-60120-452 must concur with the EOS Visit and the study intervention administration schedule of the parent study in order to ensure palovarotene treatment continuity for both chronic and flare-up treatment.

The dose of palovarotene administered will be individualised for each participant and based on the regimen (chronic or flare-up treatment), the weight and the dose received during their participation in the parent study at the time of transition to Study CLIN-60120-452 or prior to interrupting/stopping palovarotene treatment (to allow for dose modifications made to the standard chronic/flare-up regimen during the parent study)

Chronic/flare-up regimen:

**Chronic treatment:** oral palovarotene once daily, 5 mg, or at the dose received during participation in the parent study at the time of transition Study CLIN-60120-452 or prior to interrupting/stopping palovarotene treatment.

**Flare-up treatment:** increase in dose at the time of a flare-up (or substantial high risk traumatic event likely to lead to a flare-up) to 20 mg once daily for 4 weeks (28 days), followed by 10 mg once daily for 8 weeks (56 days) for a total of 12 weeks (84 days) even if symptoms resolve earlier.

Participants receiving flare-up treatment at the time of transition to Study CLIN-60120-452 will continue and complete the flare-up treatment as was planned in the parent study.

Flare-up treatment should begin at the onset of the first symptom indicative of a FOP flare-up or substantial high risk traumatic event likely to lead to a flare-up. Chronic treatment should cease at the time of initiation of flare-up treatment, re-initiation of the chronic daily treatment should occur after completion of the flare-up treatment.

**Persistent flare-up symptoms:** treatment may be extended in 4-week intervals with 10 mg palovarotene and continued until the flare-up symptoms resolve.

**Intercurrent flare-up:** if the participant experiences an intercurrent flare-up (new flare-up location or marked worsening of the original flare-up) at any time during the flare-up treatment, then the 12-week flare-up treatment should be restarted.

In the case of any intolerable adverse reactions, the daily dose of the chronic/flare-up regimen can be reduced.

## 2.3 Sample Size Determination and Power

No formal sample size calculations have been performed as the sample size is dependent on the number of participants in the parent studies who are eligible. A maximum of 87 participants from studies PVO-1A-301, PVO-1A-202/PVO-1A-204 are eligible to be enrolled.

**2.4 Randomisation and Blinding**

This is a non-randomised open-label study therefore no procedures for blinding are applicable.

**2.5 Schedule of Assessments**

The schedule of Activities (SoA) planned in this study are presented in Table 1.

Table 1 Schedule of Activities

Assessment/Procedure	Inclusion Visit[a] Day 1			Follow-Up Visits Every 6 months ( $\pm 1$ month)[b]/ EOS/EW Visit[c]	
	Procedures already performed at the parent EOS Visit that will be transferred from parent study database	Procedures already performed at the parent EOS Visit to be entered in CLIN-60120-452 eCRF by the study site	Procedures to be performed at the CLIN-60120-452 Inclusion Visit	In-clinic Visit	Remote visit
Informed consent[d]			X		
Inclusion/exclusion criteria			X		
Study intervention administration/accountability[e]			X	X	X
Baseline demographics			X		
Physical examination			X		
Participant interview[f]			X		
Pregnancy testing and childbearing potential [g]		X[a]*		X	X
Linear height and body weight [h]		X[a]*		X	X
Vital signs [i]		X[a]*		X	X
Spinal health assessment [j]		X [a]**		X	
Lung function assessments [k]			X	X	
Flare-up assessment [l]			X	X	X [m]
Additional Extra bone growth assessment (without associated flare-up)			X	X	X
CAJIS [n]	X*			X	X
C-SSRS [n] [o]			X	X	X
FOP-PFQ assessment[p] [q]	X*		X [q]***	X	X
PROMIS Global Health Scale [p][q]	X*		X [q]***	X	X
FOP assistive devices assessment [p]			X	X	X
Healthcare Utilization [p]			X	X	X
Biochemistry (amylase, lipase, AST, ALT) and triglycerides	X*				
Disease and flare-up history	X				
Prior medications	X				
Concomitant medications		X		X	X
Concomitant procedures [r]		X		X	X
AEs [s]		X		X	X

AE=adverse event; ALT=alanine aminotransferase; AST=aspartate aminotransferase; CAJIS=Cumulative Analogue Joint Involvement Scale for FOP; COVID-19=coronavirus disease 2019; C-SSRS=Columbia-Suicide Severity Rating Scale; DLCO=diffusion capacity of the lung for carbon monoxide; eCRF=electronic case report form; EOS=End of Study; EW=Early Withdrawal; FEV1=forced expiratory volume in one second; FVC=forced vital capacity; FOP=fibrodysplasia ossificans progressiva; FOP-PFQ=FOP Physical Function Questionnaire; PROMIS=Patient Reported Outcomes Measurement Information System.

a. The Inclusion Visit should be in-clinic and corresponds ideally to the EOS Visit of the parent study (Study PVO-1A-301 or PVO-1A-202/PVO-1A-204). A maximum of one month is allowed between the two visits. For any assessments from the parent EOS Visit performed outside this allowed time window, assessments will need to be performed again at the Study CLIN-60120-452 Inclusion Visit (flagged with \*). However, to enable continued access to the Investigational Product and rollover of participants with impaired mobility [in the case(s) when per investigator's judgement this is considered as beneficial for the participant's medical conditions], the parent EOS Visit and consenting for CLIN-60120-452 and CLIN-60120-452 Inclusion Visit can be conducted remotely. In such case(s) both parts of remote consenting used by the site – i.e. Informing/Consenting discussion and ICF signature should be agreed with the IRB/EC, and the investigator's judgement should be sufficiently documented in the patient source notes.

For the spinal health assessment, a time window of 3 months post parent visit is allowed (flagged with \*\*).

b. Follow-up Visits will be either in-clinic or performed remotely (e.g. at the participant's home by qualified SP in-home services, and/or via video-conference or telephone contact from clinical site personnel).

c. The EOS/EW Visit will be ideally an in-clinic visit (or remotely when permitted by the IRB/IEC) and will occur at the time of last study intervention intake. The EOS Visit must take place before the participant transitions to commercial treatment.

d. For participants <18 years, assent and legal guardian's consent will also be required.

e. Palovarotene status (treated or not treated) and regimen (chronic or flare-up treatment) at the time of transition to Study CLIN-60120-452 will be collected at the Inclusion Visit. Participants will be supplied with chronic treatment as well as the appropriate dose of palovarotene to initiate flare-up treatment when a flare-up or traumatic event is confirmed by the investigator. Participants will be instructed to report potential flare-up symptoms to study site personnel, only one symptom is required to define a flare-up (see Section **Error! Reference source not found.** of the protocol). In the presence of persistent flare-up symptoms, treatment may be extended in 4-week intervals until the flare-up symptoms resolve. If the participant experiences an intercurrent flare-up, or substantial high-risk traumatic event likely to lead to a flare-up, at any time during the flare-up treatment, the 12-week flare-up treatment should be restarted.

f. Participant interviews will be conducted in person or by telephone by the PI/qualified site staff and can be carried out anytime within 1 year (ideally within 1 month) following the Inclusion Visit.

g. Participants will be assessed for child-bearing status and pregnancy prevention measures (females only). According to local practice, medically documented blood or urine pregnancy tests should be carried out prior to starting therapy, monthly as long as the participant receives palovarotene and one month after stopping (the results of pregnancy tests will be recorded in the eCRF). See Section 8.2.6 and 8.3.5 of the protocol for procedure in case of a positive pregnancy test during the study.

h. For linear height, data from the parent EOS Visit will be used for the Study CLIN-60120-452 Inclusion Visit when available. Height at 6 to 12 months prior to the Inclusion Visit will be transferred from parent study database.

i. Vital signs to be collected are respiratory rate, blood pressure and heart rate.

j. The spinal health assessment must be performed at the Study CLIN-60120-452 Inclusion Visit ONLY if not already performed within the time window allowed (ie., 3 months post-parent EOS Visit). The spinal health assessment will then be performed annually. The spinal health assessment should be performed using radiological imaging (e.g., CT, x-ray, scintigraphy, etc). This assessment may be performed locally.

k. Includes spirometry and the DLCO test. Spirometry obtains the lung function parameters of observed and % predicted FVC and FEV1 and the absolute and predicted FEV1/FVC ratio. The DLCO test obtains observed and % predicted DLCO which provides information on the efficiency of gas transfer from alveolar air into the bloodstream.

l. Includes extra bone growth assessment when associated with a flare-up

m. During remote visit performed at home by the SP in-home services, the participant will be asked if any flare-ups occurred since last visit. If yes, the homecare clinician will attempt to facilitate a call between the participant and the site to provide details.

n. In case of remote visit, the CAJIS and C-SSRS will be assessed via video-conference if possible or feasible or telephone contact from clinical site personnel. The homecare clinician will facilitate the call between the participant and Investigator.

o. 'Baseline' version of C-SSRS will be used at the Study CLIN-60120-452 Inclusion visit. 'Since Last Visit' version of C-SSRS will be used at Follow-Up Visits.

p. In case of remote visit, the questionnaires will be provided by the SP in-home services and completed by the participants.

q. Paper patient-reported questionnaires. Questionnaires completed at the parent EOS Visit will be used for the Study CLIN-60120-452 Inclusion Visit. The adult form (developed for participants  $\geq 15$  years old) of the FOP-PFQ and PROMIS Global Health Scale will be used for all participants. At in-clinic visits when multiple assessments are to be performed, the FOP-PFQ and the PROMIS Global Health Scale should be completed first, and in that order, before any other assessments are completed. Participants who completed the paediatric versions of the questionnaires at the EOS Visit of the parent study are required to complete the adult versions of the questionnaires at the CLIN-60120-452 Inclusion Visit (flagged with \*\*\*).

r. Any vaccinations received during the study (including COVID-19) should be recorded as concomitant procedures.

- s. AEs first occurring during participation in the parent study and ongoing at the time of the Study CLIN-60120-452 Inclusion Visit will be entered again in the Study CLIN-60120-452 eCRF.

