Route of Administration	Oral
Use	Active study intervention
IMP and NIMP/AMP.	IMP
Sourcing	Centrally by sponsor

Packaging and Labelling	
Study intervention will be provided in bottle or blister packaging:
 
 - 90 capsules packaged in a bottle (1 mg, 1.5 mg, 2.5 mg, 5 mg and 10 mg). - 14 capsules packaged in a blister (1 mg, 1.5 mg and 5 mg) - 15 capsules packaged in a bottle (5 mg) for US patients only. 
Each carton will be labelled as required per country requirement.

Storage requirements	To be stored at room temperature (between 15°C and 30°C) and protected from light and humidity.
Former Names/Alias(es)	None

AMP=auxiliary medicinal product; FOP= fibrodysplasia ossificans progressiva; IMP=investigational medicinal product; NIMP=non investigational medicinal product.

Participants will be instructed to report potential flare-up symptoms to study site personnel. Only one symptom is required to define a flare-up. If these symptoms are consistent with previous flare-ups, include a participant-reported onset date, and are confirmed by the investigator as associated with a flare-up, participants will immediately begin flare-up-based treatment. Flare-up based treatment should also be initiated if the investigator confirms the presence of a substantial high-risk traumatic event likely to lead to a flare-up.

Based on clinical signs and symptoms as determined by the investigator, flare-up treatment may be extended in 4-week intervals while on-treatment with 10 mg palovarotene and continue until the flare-up resolves and the 4-week extension treatment has been completed.

Participants will be supplied with chronic treatment as well as the appropriate dose of palovarotene to initiate flare-up treatment when a flare-up or traumatic event is confirmed by the investigator (during in-clinic or remote visit, or by telephone contact).

Participants will be instructed to contact study site personnel immediately in case of intolerable adverse reactions during palovarotene treatment. The investigator will assess the adverse reaction and, if appropriate, will instruct the participant to reduce the daily dose of palovarotene as described in Section 6.5. If the participant does not have the appropriate dose in his/her possession, the study site will make immediate arrangements to ship the appropriate palovarotene dose to the participant.

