## 5.6 Compliance

Compliance is defined as (total actual doses taken/total expected doses taken) x 100.

The total actual dose taken will be calculated as (total [capsules dispensed to the participant x respective dosage] – total [capsules returned x respective dosage]) by the participant across all medication kits dispensed.

If the number of returned capsules is missing from any kit, the number of returned capsules for that kit will be imputed by multiplying the number of capsules dispensed by the mean compliance observed in the MOVE study. For chronic kits (or weight-adjusted/de-escalate equivalent)  $\leq 5$ mg, a compliance of 80% will be used estimate the number of capsules returned. For flare-up kits (or weight-adjusted/de-escalate equivalent)  $> 5$ mg, a compliance of 87% will be used to estimate the number of capsules taken for that kit. These imputed values will then be used to determine the overall dose taken across the duration of the study.

The total expected dose taken will be calculated by multiplying the duration of treatment in days for each treatment regimen, across all cycles of that regimen, (see derivation under section 5.6.6) by the planned dose for each regimen and finally totalling the expected dose across all regimens.

The expected duration of treatment is calculated as following for each treatment regimen:

Total of expected regimen cycle dosing periods across all regimen cycles. Each expected regimen cycle dosing period is defined as (last regimen cycle dose date – first regimen cycle dose date + 1).

Compliance will be summarised for the FAS/SAS set with descriptive statistics. Compliance in each category (<80%, ≥80% - ≤120%, >120%) will also be summarised for counts and percentages of participants.

A listing of treatment compliance, including all derived parameters will be provided.

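### SAP 5.6 imputes use of an uncounted kit from bottle contents without checking for a matching course, so the compliance summary can be wrong

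*SAP*

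**What the plan says.** **Supply.** SAP 2.5 (Table 1, footnote e) says: "Participants will be supplied with chronic treatment as well as the appropriate dose of palovarotene to initiate flare-up treatment". The same statement is in note b to the study schema (SAP 2.2) and in Protocol 6.1. Protocol 6.1 adds that, once the investigator confirms a flare-up, "participants will immediately begin flare-up-based treatment".

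**Pack size.** Protocol 6.1, Table 4, lists "90 capsules packaged in a bottle (1 mg, 1.5 mg, 2.5 mg, 5 mg and 10 mg". The 10 mg strength is the only one above 5 mg, and the 90-capsule bottle is its only listed pack.

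**Compliance.** SAP 5.6: "Compliance is defined as (total actual doses taken/total expected doses taken) x 100". The numerator is milligrams dispensed minus milligrams returned, summed "by the participant across all medication kits dispensed". The denominator is days on each regimen times the planned dose for that regimen, totalled over regimens.

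**Missing counts.** The imputation starts with "If the number of returned capsules is missing from any kit". Its lead sentence obtains capsules *returned* as dispensed times mean compliance, and the sentence on chronic kits (80%) also refers to capsules returned. The sentence on flare-up kits above 5 mg says instead that "a compliance of 87% will be used to estimate the number of capsules taken for that kit". Compliance is then reported with descriptive statistics, in three classes (below 80%, 80 to 120%, above 120%) and in a listing.

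**The concern.** A compliance percentage describes the share of *required* doses that were taken. SAP 5.6 applies it to the *contents of a bottle*, whether or not the bottle was needed. For a kit held in case of a flare-up that never came, the numerator gains milligrams and the denominator gains nothing. A correctly dosed participant can then appear in the above-120% class, and a poor complier can be lifted into the 80 to 120% class. For kits that were used, the imputed amount depends on how many bottles happened to be uncounted and not on the length of the course. A reader of the study report would take the above-120% class as a sign of excess dosing, so false entries there matter even in a purely descriptive study.

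**Working it through.** The plan gives no worked compliance figure to reproduce, so the SAP 5.6 formula is applied directly.

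**Inputs**
- Chronic dose: 5 mg once daily (SAP 2.2).
- Flare-up course: 20 mg for 28 days, then 10 mg for 56 days (SAP 2.2).
- Bottle: 90 x 10 mg = 900 mg (Protocol 6.1).
- Imputed fraction taken, f: 0.87 on the *taken* sentence; 1 − 0.87 = 0.13 on the *returned* sentence.
- Assumed, because not stated: one unused, uncounted standby bottle, with other quantities shown as a range; all chronic kits counted.

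**Unused kit.** For a flare-free participant who takes every 5 mg dose for D days, with K uncounted 10 mg capsules:

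compliance = 100 x (5D + 10 f K) / (5D)

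This exceeds 120% when D < 10 f K / (0.2 x 5) = 10 f K.

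One bottle adds 0.87 x 900 = 783 mg (*taken*) or 0.13 x 900 = 117 mg (*returned*). At 365 days the expected dose is 5 x 365 = 1825 mg, so the scores are (1825 + 783)/1825 = 142.9% and (1825 + 117)/1825 = 106.4%. In the same way:

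| Uncounted capsules | Reading | 365 days | 730 days | 1095 days | Over 120% before day |
|---|---|---|---|---|---|
| 56 (28 days at 20 mg) | taken | 126.7% | 113.3% | 108.9% | 487 |
| 90 (one bottle) | taken | 142.9% | 121.5% | 114.3% | 783 |
| 112 (one full course) | taken | 153.4% | 126.7% | 117.8% | 974 |
| 180 (two bottles) | taken | 185.8% | 142.9% | 128.6% | 1566 (beyond the study) |
| 90 (one bottle) | returned | 106.4% | 103.2% | 102.1% | 117 |
| 180 (two bottles) | returned | 112.8% | 106.4% | 104.3% | 234 |

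The true value in every cell is 100%.

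**Masking.** With true chronic compliance of 60% over 365 days, 0.60 x 1825 = 1095 mg was taken. One uncounted bottle gives (1095 + 783)/1825 = 102.9% on the *taken* reading, which falls in the 80 to 120% class. On the *returned* reading it gives (1095 + 117)/1825 = 66.4%, which stays below 80%.

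**Used kit.** A full course needs 28 x 2 + 56 x 1 = 112 capsules of 10 mg. On the *taken* reading, and looking at the flare-up component alone:
- one uncounted bottle as the only flare-up kit counted: 0.87 x 90 = 78.3 capsules, and 78.3/112 = 70%;
- two uncounted bottles: 0.87 x 180 = 156.6 capsules, and 156.6/112 = 140%.

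The result follows the number of bottles, and the error can go in either direction.

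**The case against.** **Advance supply is an inference.** The longer run of the sentence is "Participants will be supplied with chronic treatment as well as the appropriate dose of palovarotene to initiate flare-up treatment when a flare-up or traumatic event", and it ends by requiring the investigator's confirmation. That clause could govern the supply and not only the start of treatment, and Protocol 6.2 allows dispensing at unscheduled visits. The context still favours standby stock. Treatment starts immediately on confirmation, confirmation may be by telephone, and the only shipping step described in Protocol 6.1 is for a reduced dose. A reader might go further and infer that many flare-up kits are never opened. Nothing in the documents gives that proportion.

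**The size depends on a contradiction.** On the *returned* reading, one bottle passes 120% only before day 117, and at 12 months even two bottles give 112.8%. This stands. The large figures belong to the *taken* sentence only, and the section must be reconciled first. Neither reading removes the fault, because 13% of an unused kit still counts as swallowed.

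**The trigger may be rare.** Protocol 6.4 requires kits to be brought back and counted, and Protocol 6.2 adds paper records. This also stands, although remote visits make gaps foreseeable and the SAP provides for them.

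**The used-kit figures are simplified.** Extensions and restarts would use more capsules and enlarge the denominator. The 70% and 140% show that the error can take either sign; they do not measure its typical size.

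**Safety results are not affected.** A reader might infer that the rule misstates the exposure behind the primary safety endpoint. The documents do not support that. SAP 5.8.2 derives treatment duration from dosing-form and contact dates, SAP 5.7.2.2 takes dose at adverse-event onset from the dosing log, and the analysis set requires only one dose. Whether compliance affects the per-protocol set depends on the Protocol Deviation Plan, which is not among the documents.

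**Conclusion.** The rule is wrong as written, within a limited scope. SAP 5.6 imputes from bottle contents without checking that the kit was used, against a denominator that counts only regimens actually dosed. For a fully adherent, flare-free participant with one unused, uncounted 10 mg bottle, the *taken* sentence gives 142.9%, 121.5% and 114.3% at 12, 24 and 36 months, over 120% until day 783. The *returned* sentence gives 106.4% at 12 months, over 120% only before day 117. For used kits the error has no fixed direction.

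This rests on three assumptions: flare-up drug is held ahead of need, the standby quantity lies in the range shown, and some return counts are missing. The 87% rule covers only kits above 5 mg, so flare-up supply made up of smaller capsules falls outside it. What is affected is the compliance mean, the three classes and the listing. Exposure duration and the adverse-event tables do not use capsule counts.

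**What to change.** In SAP 5.6:

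1. State whether the 80% and 87% apply to capsules returned or to capsules taken, and use one wording for both kit types.
2. Impute only for kits whose strength and regimen match a dosing-form record after the dispensing date.
3. For those kits, impute capsules taken as 80% or 87% of the capsules the dosing form required over the period, capped at the number dispensed.
4. Leave an uncounted flare-up kit with no matching course out of dose taken, and list it as unaccounted for. Simply setting it to zero would hide possible unrecorded use; the listing keeps that visible.
5. Correct the pointer to section 5.6.6, which the SAP does not contain; the duration derivations are in 5.8.2.

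With step 4, the example participant scores 5D/5D = 100% at every duration.

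The cost is a few lines of SAP text and a merge of accountability data with the dosing form. Both are already collected, and SAP 5.7.2.2 already merges the dosing log with adverse-event dates. Accountability is held in source documents and the interactive web response system, so a data transfer may be needed. No new data collection is required.
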